1.0 Background of the Surveillance

Since the amount of leuprorelin acetate administered in a single dose of Leuplin PRO for Injection Kit 22.5 mg (hereinafter referred to as Leuplin PRO) is as high as twice that of Leuplin SR for Injection Kit 11.25 mg (hereinafter referred to as Leuplin SR), and the time profile of serum leuprorelin concentration after administration differs between the two formulations, a special drug use surveillance (hereinafter referred to as the surveillance) is planned to evaluate potential effects of the differences on the safety.

This surveillance will be conducted in compliance with the ministerial ordinance on Good Post-Marketing Study Practice (GPSP) and related regulatory requirements.

2.0 Objectives

To investigate the safety of Leuplin PRO in patients with prostate cancer in routine clinical settings in order to evaluate potential effects of differences between Leuplin PRO and Leuplin SR, including the higher amount administered in a single dose and differences in time profile of serum drug concentration after administration, on the safety

3.0 Planned Sample Size and Rationale

3.1 Planned Sample Size

300 patients

3.2 Rationale

To evaluate potential effects of differences between Leuplin PRO and Leuplin SR, that is, difference amounts of leuprorelin acetate administered in a single dose and different time profiles of serum drug concentration after administration, on the safety, it was decided to investigate the occurrence of injection site reaction and other adverse drug reactions (ADRs) with an incidence of 1% or higher, including the time of onset, incidence, and seriousness.

The sample size of 300 patients was determined to detect ADRs with an incidence of 1% or higher at a probability of 95% or higher.

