8.0 Planned Surveillance Period

Surveillance period: From April 2016 to 30 September 2017

Patient registration period: From April 2016 to 31 March 2017^{Note)}

^{Note)} Patient registration (entry into **CCI**) will not be accepted on 1 April 2017 onwards even if Leuplin PRO is administered by 31 March 2017.

If the number of patients enrolled in the surveillance reaches the planned sample size before 31 March 2017, acceptance of registration will be terminated before the end of the patient registration period. If the patient registration period is shortened, the surveillance period will be changed accordingly.

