1.1 List of Terms and Abbreviations

- Leuplin PRO: Leuplin PRO for Injection Kit 22.5 mg is abbreviated as Leuplin PRO.
- Adverse drug reaction (ADR), etc.: ADR, etc. is an abbreviation of ADR/infection. ADRs, etc. refer to all adverse events (AEs) other than those assessed by the investigator to be not related to Leuplin PRO. In this document, “adverse drug reactions/infections” is used in titles, and “ADRs, etc.” is used in the text and tables.
- Serious adverse event (SAE): A SAE is an adverse event assessed by the investigator to be serious. Events included in the MedDRA code list in Takeda Medically Significant AE List will be handled as serious even if assessed by the investigator to be not serious.
- Causal relationship: An event assessed as not related to Leuplin PRO will be handled as “not related.” Events not unrelated to Leuplin PRO in the text and tables refer to all events other than those assessed as not related to Leuplin PRO.
- Summary statistics: Collective term for number of patients, mean, standard deviation, maximum, minimum, and quartiles
- Patient with no CRF collected: Enrolled patient for whom the CRF has not been collected
- Patient with the CRF collected: Enrolled patient for whom the CRF has been collected
- Finalized patient: Patient for whom the CRF has been collected and finalized at least once by data lock point
- Non-finalized patient: Patient for whom the CRF has been collected, but has not been finalized by data lock point
- Age: If the month and day of starting Leuplin PRO treatment is smaller than the month and day of birth, age will be calculated as year of starting Leuplin PRO treatment - year of birth - 1. If the month and day of starting Leuplin PRO treatment is equal to or greater than the month and day of birth, age will be calculated as year of starting Leuplin PRO treatment - year of birth. If the day of birth is unknown, 1 will be used for calculation.
- Time from diagnosis of prostate cancer to patient registration (months):
 - Actual number (units: month) = (“date of patient registration” - “date of diagnosis” + 1)/30.44
- BMI (kg/m^2): Calculated as body weight (kg)/height (m)² (displayed to one decimal place by rounding)

- Induration: AE with “induration” selected for “Specific symptom (multiple answers allowed)” in the column of [Adverse event: Injection site reaction] in the CRF
- Prostate cancer drug other than luteinizing hormone-releasing hormone (LH-RH) agonists or antagonists

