1.2 Analysis Sets

The analysis set in this surveillance is safety population. This analysis set is defined as described below.

- Safety population

In this document, the safety population is defined as all Leuplin PRO-treated patients evaluable for safety with no major protocol violation. Patients for whom the CRF has been collected will be excluded from the safety population if any of the following criteria is met:

- Not treated with Leuplin PRO
- Treatment before the contract period
- Registration 15 days or more after Leuplin PRO treatment
- It is unknown whether the patient experienced an AE

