2.1 Disposition of Patients

Patients included All enrolled patients (enrolled patients) in analysis:

Analysis items: Enrolled patients

Number of surveillance medical institutions

Patients with no CRF collected

Reason for failure to collect

[Transfer of the investigator during the observation period, medical reason for the investigator, other]

Patients with the CRF collected

Non-finalized patients

Finalized patients

Patients excluded from safety evaluation*

Reason for exclusion (multiple tabulation)

[Not treated with Leuplin PRO, treatment before the contract period, registration 15 days or more after Leuplin PRO treatment, it is unknown whether the patient experienced an AE]

Patients included in safety evaluation*

Analysis methods: For the aforementioned analysis items, analysis will be performed as described below, and a patient composition diagram will be prepared.

For enrolled patients, the number of surveillance medical institutions will also be calculated. One medical institution with different departments will be counted as one medical institution.

* Patients included in safety evaluation refer to the safety population, and patients excluded from safety evaluation refer to patients excluded from the safety population (finalized patients excluded from the safety population here).

(1) Frequency tabulation

3 Patient Baseline Characteristics

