5.1.2 Occurrence of Adverse Drug Reactions/Infections

Patients included Safety population

in analysis:

Analysis item: ADRs, etc.

Analysis methods: For the aforementioned analysis item, analysis will be performed as described below.

- (1) Number of patients with an ADR, etc.
- (2) Number of ADR, etc.
- (3) Incidence of ADR, etc.
- (4) Type of ADR, etc.

For each analysis, events or patients will be counted as described below.

[Number of patients with an ADR, etc.]

- Number of patients who experienced an ADR, etc.

[Number of ADR, etc.]

- Number of reported ADR, etc. Multiple episodes of the same ADR, etc. in the same patient will be tabulated as the total number of episodes.

[Incidence of ADR, etc.]

- The incidence of ADR, etc. will be calculated as number of patients with an ADR, etc./number of patients included in safety evaluation $\times 100$.

[Type of ADR, etc.]

- ADRs, etc. will be coded using the MedDRA/J. ADRs, etc. will be classified by SOC and then tabulated by PT. For the SOC of investigations, ADRs, etc. will be sorted by HLGT (lined up in ascending order of HLGT code, but not output) and then tabulated by PT.
- For SOC, the number and incidence of ADR, etc. will be listed in internationally agreed SOC order. Multiple episodes of the same SOC in the same patient will be counted as 1 patient for the relevant SOC.
- For PT, the number and incidence of ADR, etc. will be listed in ascending order of PT code. Multiple episodes of the same PT in the same patient will be counted as 1 patient for the relevant PT.

5.1.3 Occurrence of Adverse Events Corresponding to Important Identified Risks, Important Potential Risks, or Important Missing Information

Patients included Safety population

in analysis:

Analysis item: AEs corresponding to important identified risks, important potential risks, or important missing information (described in Section 1.4 in Section 1, “Definitions of Terms, etc.”)

Analysis methods: For the aforementioned analysis item, analysis will be performed as described below.

- (1) Number of patients with an AE
- (2) Number of AE
- (3) Proportion of patients with an AE
- (4) Type of AE

For each analysis, events or patients will be counted as described below.

[Number of patients with an AE]

- Number of patients who experienced an AE

[Number of AE]

- Number of reported AE. Multiple episodes of the same AE in the same patient will be tabulated as the total number of episodes.

[Proportion of patients with an AE]

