5.6 Summary of Patients in Post-Marketing Surveillance, etc. (Attachment Style 16)

Patients included Patients with the CRF collected

in analysis:

Analysis items: Patient number

Site name

Sex

Date of birth

Reason for use (disease code, disease name)

Concurrent illness (disease code, disease name)

Route of administration

Maximum dose

Mean dose

Units

Duration of use

Concomitant medication (NHI drug code, drug name)

Degree of response

ADR (disease code, disease name, outcome)

CRF number

Dropout

Analysis methods: The aforementioned analysis items will be listed in accordance with Notes 1 to 3 in Attachment style 16 in Notification concerning re-examination,

PSEHB/PAB/ED Notification No. 1128-2 dated 28 November 2017.

Attached table PTs corresponding to risks

Risk	PT code	PT
Injection site reaction	10022044	Injection site abscess
	10068791	Administration site abscess
Decreased bone mass density	10000397	Acetabulum fracture
	10002544	Ankle fracture
	10009245	Clavicle fracture
	10009506	Closed fracture manipulation
	10010149	Complicated fracture
	10010214	Compression fracture
	10014487	Elevation skull fracture
	10015741	External fixation of fracture
	10016042	Facial bones fracture
	10016450	Femoral neck fracture
	10016454	Femur fracture
	10016667	Fibula fracture
	10016970	Foot fracture
	10016997	Forearm fracture
	10017076	Fracture
	10017081	Fracture delayed union
	10017085	Fracture malunion
	10017088	Fracture nonunion
	10017107	Fracture of clavicle due to birth trauma
	10017290	Fractured ischium
	10017296	Fractured maxilla elevation
	10017308	Fractured sacrum
	10017310	Fractured skull depressed
	10018720	Greenstick fracture
	10019114	Hand fracture
	10020100	Hip fracture
	10020462	Humerus fracture
	10021343	Ilium fracture
	10022576	Internal fixation of fracture
	10023149	Jaw fracture
	10028200	Multiple fractures
	10030527	Open fracture

Risk	PT code	PT
	10030682	Open reduction of fracture
	10030684	Open reduction of spinal fracture
	10031290	Osteoporotic fracture
	10034122	Patella fracture
	10034156	Pathological fracture
	10037802	Radius fracture
	10039117	Rib fracture
	10039579	Scapula fracture
	10040960	Skull fractured base
	10041541	Spinal compression fracture
	10041569	Spinal fracture
	10042015	Sternal fracture
	10042212	Stress fracture
	10043827	Tibia fracture
	10045375	Ulna fracture
	10048049	Wrist fracture
	10049164	Fractured coccyx
	10049514	Traumatic fracture
	10049946	Cervical vertebral fracture
	10049947	Lumbar vertebral fracture

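### Does the 95% chance of seeing a 1% ADR fail because 300 counts enrolled rather than evaluable patients?

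*Protocol*

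**What the plan says.** Protocol 3.1 plans 300 patients, and 3.2 gives the only quantitative reason: "300 patients was determined to detect ADRs with an incidence of 1% or higher at a probability of 95% or higher". The text does not define detection and mentions no losses.

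Protocol 8.0 ties the planned number to enrolment: "If the number of patients enrolled in the surveillance reaches the planned sample size before 31 March 2017, acceptance of registration will be terminated".

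SAP 5.1.2 defines ADR incidence as a percentage, "number of patients with an ADR, etc./number of patients included in safety evaluation". Patients can drop out between enrolment and that denominator at three points:

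- No CRF is collected (SAP 1.1 and 2.1).
- The CRF is not finalized. SAP 1.1 defines this group as "Patient for whom the CRF has been collected, but has not been finalized by data lock point". SAP 2.1 appears to take the safety population from finalized patients only, because its footnote describes the excluded group as "finalized patients excluded from the safety population here".
- A ground in SAP 1.2 applies: "Patients for whom the CRF has been collected will be excluded from the safety population if any of the following criteria is met". The four grounds are no treatment, treatment before the contract, late registration and unknown AE status.

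SAP 5.6 uses a wider set for its patient listing, which includes ADRs. Its analysis-set line reads "Patients included Patients with the CRF collected" (row label and entry run together).

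**The concern.** A sample size justified by a detection probability should refer to the patients in whom detection is assessed. Here 300 is the number at which registration closes, while incidence is reported on a set that can only be the same size or smaller. The minimum that satisfies the 95% criterion is 299, so the literal margin is one patient. About 60 institutions follow patients for 24 weeks in routine care, and it would be surprising if no more than one patient failed to reach the safety population.

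At stake is the accuracy of one sentence. If the report repeated the 95% and 1% figures without comment, it might credit the analysed set with slightly more than it can deliver.

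**Working it through.** **Inputs.** Planned n = 300 (Protocol 3.1). True incidence p = 1% and target probability 95% (Protocol 3.2). The documents give no loss rate.

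**Reproducing the plan's figure.** The probability of at least one case among n patients is 1 − (1 − p)^n.

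- At n = 300: 1 − 0.99^300 = 95.10%.
- Smallest adequate n: ln(0.05)/ln(0.99) = 298.07, so 299.
- Poisson form: −ln(0.05)/0.01 = 299.57, so 300.
- Rule of three: 3/0.01 = 300.

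The stated figure reproduces by all three routes.

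**What detection means.** With n = 300 and p = 1%, the chance of at least two cases is 80.2% and of at least three is 57.8%. Of these readings only at least one case meets the 95% in 3.2, so the missing definition leaves no practical doubt.

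**Effect of losses.** The fourth column is the incidence that n patients would show at least once with 95% probability, 1 − 0.05^(1/n).

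| Lost of 300 | n | P(at least one case) at 1% | Incidence detectable at 95% |
|---|---|---|---|
| 0 | 300 | 95.10% | 0.99% |
| 1 | 299 | 95.05% | 1.00% |
| 2 | 298 | 94.996% | 1.0002% |
| 15 (5%, assumed) | 285 | 94.30% | 1.05% |
| 20 | 280 | 94.00% | 1.06% |
| 30 (10%, assumed) | 270 | 93.37% | 1.10% |
| 45 (15%, assumed) | 255 | 92.29% | 1.17% |
| 70 | 230 | 90.09% | 1.29% |

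The criterion is first missed at 298, by 95 − 94.996 = 0.004 percentage points. A loss of 70 patients, nearly a quarter of the cohort (70/300 = 23%), still leaves 90%.

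**Which losses affect detection.** Protocol 7.3 registers patients after the injection and within 14 days. No treatment, treatment before the contract and late registration would therefore be departures from the protocol. Presence or absence of AEs is a required item (Protocol 9.4), so unknown AE status is a data failure. Stopping observation early is tabulated within the safety population (SAP 4.3) and is not an exclusion.

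Detecting an ADR is also different from counting a patient in the denominator. An ADR in a patient excluded for late registration or pre-contract treatment still appears in the SAP 5.6 listing, as does one on a collected but non-finalized CRF. The routine loss that removes a patient from view altogether is mainly the CRF that is never collected.

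**The case for a change.** The strongest case for a change runs as follows. The criterion in 3.2 is 95% or higher, not roughly 95%. The plan itself foresees losses, since Protocol 10.3 and SAP 2.1 list enrolled, CRF-collected, excluded and included patients separately. Some of these losses are not breaches of the registration rule: an investigator may transfer, or a CRF may not be finalized in time. A margin of one patient is in effect no allowance. The usual practice is to inflate: to keep 299 evaluable patients, 299/0.95 = 314.7, so 315, at an assumed 5% loss, or 299/0.90 = 332.2, so 333, at 10%. The SAP 5.6 listing is not the incidence denominator and omits patients without a CRF. A clarifying sentence would cost almost nothing.

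Most of this stands as fact. The enrolled count, the missing allowance and the literal margin of one patient are all correct. The loss of non-finalized patients is probable, but it is inferred from the layout and footnote of SAP 2.1; SAP 1.2 does not list it as an exclusion.

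What does not follow is that the plan must change. Labelling 299 as a safety-population number adds no patients. A detection probability for the achieved n is 1 − 0.99^n, which a reader can compute from the SAP 2.1 counts. Once data are in, the observed incidence and its denominator say more than a retrospective detection probability.

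**Conclusion.** The concern does not call for a change. The sample-size statement is arithmetically correct, and its aim, "to detect ADRs with an incidence of 1% or higher", is met to within about one percentage point unless more than 20 of 300 patients are lost. Followed as written, the plan gives the same tables and the same conclusions with or without the clarification, because no test, stopping rule or decision uses the 95%.

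This is a small gap in wording that analysts fill sensibly: the report gives the size of the safety population, and the reader judges detectability from that. If the author wishes, 3.2 could say that the figure refers to evaluable patients, and the report could give 1 − 0.99^n beside the planned rationale. Neither is needed.

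The conclusion assumes that detection means at least one case, that patients are independent with a common 1% risk, and that losses are not very large. The documents give no loss rate, and the 5% to 15% range is illustrative only. Losses well beyond 70 patients would take the probability below 90%, but SAP 2.1 would show that openly.

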4.0 Surveillance Population

Patients with prostate cancer will be included in the surveillance. Patients should not meet the exclusion criterion listed below. Refer to the Precautions section of the package insert.

<Exclusion criteria>

Patients who meet the following criterion will not be included:

- A history of hypersensitivity to any of the ingredients of Leuplin PRO or synthetic luteinizing hormone-releasing hormone (LH-RH) or LH-RH derivatives

5.0 Dosage and Administration

The usual adult dosage is 22.5 mg of leuprorelin acetate administered subcutaneously once every 24 weeks. Refer to the Precautions section of the package insert.

6.0 Planned Number of Medical Institutions by Department

| | |
|-------------------------------|---------------------------------------|
| Urology and other departments | Approximately 60 medical institutions |
|-------------------------------|---------------------------------------|

7.0 Methodology

7.1 Observation Period

24 weeks

7.2 Request to and Contract with the Study Site

This surveillance will be conducted using a Web-based electronic data capture system (CCI [REDACTED]). A representative of Takeda Pharmaceutical Company Limited (hereinafter referred to as Takeda's representative) will explain the objectives and contents of the surveillance, operation method of [REDACTED] and handling of electronic signature, user ID, and password to the investigator based on "Request for cooperation for special drug use surveillance," "Implementation outline," "Entry screen image," and "Operation manual of [REDACTED] (brief version)" to enter into a written contract with the study site and request the study site to conduct a surveillance within a specified period.

7.3 Method of Patient Registration

Patients will be registered using the central registration method via [REDACTED]. After the start of the contract with the study site, the investigator shall register each patient treated with Leuplin PRO by entering patient registration information (refer to Section 9.1) with his/her electronic signature within 14 days after administration of Leuplin PRO (day of administration designated as day 0 and day following the day of administration designated as 1 day post-dose).

7.4 Entry into the (Electronic) Case Report Form and Electronic Signature

The investigator or designee* shall enter patient baseline characteristics and treatment given into [REDACTED] with the investigator's electronic signature within approximately 1 month after the end of required observation at 24 weeks after the

start of Leuplin PRO treatment.

For any patient with an adverse event, the investigator or designee shall enter observation results into **CCI** with the investigator's electronic signature after monitoring the patient as long after discontinuation of treatment as possible until the adverse event is confirmed to have resolved or be resolving.

* The investigator's designee should belong to the relevant medical institution (including those under contract with the medical institution such as temporary clinical research coordinators). Before the investigator's designee begins to enter data into **CCI** a physician responsible for the surveillance (one physician per medical institution or department appointed at the time of contract) shall document the designation with the date of designation (no specific style), affix his/her signature or name and seal to the document, and submit it to Takeda's representative.

8.0 Planned Surveillance Period

Surveillance period: From April 2016 to 30 September 2017

Patient registration period: From April 2016 to 31 March 2017^{Note)}

^{Note)} Patient registration (entry into **CCI**) will not be accepted on 1 April 2017 onwards even if Leuplin PRO is administered by 31 March 2017.

If the number of patients enrolled in the surveillance reaches the planned sample size before 31 March 2017, acceptance of registration will be terminated before the end of the patient registration period. If the patient registration period is shortened, the surveillance period will be changed accordingly.

9.0 Surveillance Items

The investigator or designee shall enter the items listed below into **CCI**. The surveillance schedule is presented in Appendix.

9.1 Patient Registration

1) Surveillance items

Date of administration of Leuplin PRO, patient identification number, patient initials, date of birth, assessment based on the exclusion criteria

2) Time points of surveillance

At patient registration

9.2 Patient Baseline Characteristics

1) Surveillance items

Time of diagnosis of prostate cancer, ECOG Performance Status*, disease status, diagnostic category (at the start of Leuplin PRO treatment), predisposition to hypersensitivity (presence or absence and details), concurrent

illness (presence or absence and details), history of thromboembolism (presence or absence and details), height, body weight, treatment status of prostate cancer drug immediately before the start of Leuplin PRO treatment (presence or absence and name of the drug)

2) Time points of surveillance

At the start of Leuplin PRO treatment

* ECOG Performance Status

| Score | Definition |
|-------|---|
| 0 | Fully active, able to carry on all pre-disease performance without restriction |
| 1 | Restricted in physically strenuous activity, but ambulatory and able to carry out work of a light or sedentary nature (e.g., light house work, office work) |
| 2 | Ambulatory and capable of all self-care but unable to carry out any work activities; up and about more than 50% of waking hours |
| 3 | Capable of only limited self-care; confined to bed or chair more than 50% of waking hours |
| 4 | Completely disabled; cannot carry on any self-care; totally confined to bed or chair |

(Common Toxicity Criteria, Version 2.0 Published on April 30, 1999. Webpage of the JCOG at <http://www.jcog.jp/>)

